5.6. Effectiveness Endpoints

Effectiveness endpoints will be summarized in the per-protocol population for each cohort at each study visit for which they are available. See Appendix A for a listing of scheduled assessments by visit.

Rev.02, 1 March 2018 Confidential Page 4 of 8

Document: TDOC-0056125 **Version:** 1.0; CURRENT; Most-Recent; Effective

Status: Effective

Protocol CVM-00001 Statistical Analysis Plan

ClarVista Medical, Inc.

Effective Date: 24-Jun-2019

6. Sample Size

The sample size for this study was not based on any statistical criteria. The sample size was chosen to provide sufficient experience and feedback regarding the ClarVista HARMONI™ Modular Intraocular Lens System at five investigative centers.

7. Analysis Populations

Safety Population: Eyes with attempted study lens (HMIOL) implantation, (successful or aborted after contact with the eye). The intraoperative and postoperative AEs and device deficiencies, slit lamp examination, dilated fundus examination, and IOP will be summarized based on the safety population.

Per-Protocol Population: Eyes with successful HMIOL implantation that do not have major protocol deviations (such as improperly enrolled in the study or lens power calculation errors). The effectiveness endpoints will be summarized based on the per-protocol population.

10. Interim Analyses

There are no plans for formal interim analyses for the purposes of study modification or possible early termination. Any interim analyses will be administrative in nature and results will not be distributed to Investigators or subjects to prevent bias from exposure to accruing study results.

Interim Safety Summary: Safety outcomes will be evaluated when all eyes in Cohort 1 and Cohort 2 have completed the 1 Month Visit following primary cataract extraction and optic exchange, respectively (post-optic exchange for Cohort 2).

Final Safety and Effectiveness outcomes will be evaluated when all study subjects complete the final visit or exit the study.

11. Deviations from the Statistical Analysis Plan

Any deviations from the Statistical Analysis Plan will be noted and described with appropriate statistical and clinical rationale as needed.

12. References

1. ISO 11979-7:2014 Ophthalmic implants — Intraocular lenses — Part 7: Clinical investigations.

Rev.02, 1 March 2018 Confidential Page 5 of 8

Document: TDOC-0056125 **Version:** 1.0; CURRENT; Most-Recent; Effective

Status: Effective

Protocol CVM-00001 Statistical Analysis Plan

ClarVista Medical, Inc.

Effective Date: 24-Jun-2019

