#### 8.2.1 IMPLANTED-EYE POPULATION

The Implanted-Eye Population consists of eyes with successful HMIOL implantations during surgeries.

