#### 8.2.2 PER PROTOCOL POPULATION

The **Per Protocol** (PP) Population contains eyes with successful HMIOL implantations during surgeries and do not have major protocol deviation (such as improperly enrolled in the study or lens power calculation errors) and will be considered the primary population for effectiveness outcomes.

The protocol deviations will be determined reviewed by ClarVista clinical personnel prior to analysis.

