#### 8.3.1 OUTCOMES

Each endpoint will be analyzed based on the Implanted-eye Population and PP Population.

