1 TITLE PAGE

Protocol Number: ClarVista CVM-00001

Medical Specialty: Surgical

Project Name /Number: NA

Sponsor Name & Address: CLARVISTA MEDICAL, INCORPORATED

[name]

[name] [contact] [contact]

Test Article(s) / Product(s): ClarVista HARMONI® Modular Intraocular Lens

System

Document: TDOC-0056125 **Version:** 1.0; CURRENT; Most-Recent; Effective

Status: Effective

Protocol CVM-00001 Statistical Analysis Plan

ClarVista Medical, Inc.

Effective Date: 24-Jun-2019

Statistical Analysis Plan for Protocol CVM-00001

EVALUATION OF VISUAL AND REFRACTIVE OUTCOMES OF THE CLARVISTA HARMONI™ MODULAR INTRAOCULAR LENS SYSTEM

Sponsor ClarVista Medical, Incorporated

[name]

[name] [contact] [contact]

Original Version Date 1 March 2018

Rev.02, 1 March 2018 Confidential Page 1 of 8

Document: TDOC-0056125 **Version:** 1.0; CURRENT; Most-Recent; Effective

Status: Effective

Protocol CVM-00001 Statistical Analysis Plan

ClarVista Medical, Inc.

Effective Date: 24-Jun-2019

Table of Contents

1.	Purpose	. 3
2.	Scope	. 3
3.	Software	. 3
4.	Design and Objectives	. 3
5.	Statistical Analyses	. 4
6.	Sample Size	. 5
7.	Analysis Populations	. 5
8.	Sensitivity Analyses	. 5
9.	Subgroup Analyses	. 5
10.	Interim Analyses	. 5
11.	Deviations from the Statistical Analysis Plan	. 5
12.	References	. 5
Арр	endix A – Assessment Schedule	. 6
Арр	endix B - Surgeon Questionnaire	. 7

Document: TDOC-0056125 **Version:** 1.0; CURRENT; Most-Recent; Effective

Status: Effective

Protocol CVM-00001 Statistical Analysis Plan

ClarVista Medical, Inc.

1. Purpose

This Statistical Analysis Plan documents and describes the planned analyses for the CVM-00001 study. This is a study to evaluate surgeon experience and visual and refractive outcomes of the ClarVista HARMONI™ Modular Intraocular Lens System in primary implantation and optic exchange procedure.

2. Scope

This document is based on the Investigational Plan CVM-00001, Rev.03. Changes to the Investigational Plan may require updates to this document. Analyses described here expand on and supersede those described in the Investigational Plan.

3. Software

Statistical analyses will be performed with SAS System Software version 9.4 or above (SAS Institute, Cary, N.C.), R version 3.3 or above (R Core Team, http://www.R-project.org), or other validated statistical software package.

4. Design and Objectives

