The CVM-00001 study is designed as a prospective, multi-center, cohort study. Any pre-planned formal hypothesis tests for this feasibility study are not for the purposes of generating definitive conclusions to support regulatory approval.

The study was carried out at five investigational centers, in the Philippines (3 centers), Panama (1) and Mexico (1).

The study comprises patients with planned removal of cataracts (cortical, nuclear, subcapsular, or a combination) by manual phacoemulsification. The investigator will determine if the test lens is to be implanted in OD, OS, or OU based on target refraction and the best interests of the subject.

All patients will have visits scheduled for 1 Day, 1 Week, and 1 Month following primary cataract extraction. During follow up the Investigator and Subject will decide if an optic exchange in the study eye is in the best interests of the subject based on refractive outcome and target. Subjects with satisfactory outcomes, or those opting not to pursue an optic exchange, will be entered into Cohort 1.

Subjects who opt for an HMIOL optic exchange in their primary eye will be entered into Cohort 2. Optic exchange patients will have visits scheduled for 1 Day, 1 Week, and 1 Month following the optic exchange procedure. These subjects may be followed up beyond 1 month as deemed necessary by the surgeon.

Several cohorts of subjects are specified to help characterize the clinical significance of the study outcomes in eyes with and without optic exchange. These cohorts are defined as follows:

All HMIOL Eyes Cohort: Defined as all study eyes implanted with the study device.

Cohort 1: Defined as the subset of study eyes implanted with the study device without a subsequent optic exchange procedure.

Cohort 2: Defined as the subset of study eyes implanted with the study device with a subsequent optic exchange procedure. Analysis of follow-up visits for this cohort will cover two separate time periods:

- Pre-Optic Exchange, comprising visits following primary cataract extraction, prior to the optic exchange visit (through 1 month).
- Post-Optic Exchange, comprising visits following optic exchange. The baseline for the post-optic
 exchange visits is the last pre-optic exchange visit (1-month).

Separate analyses are planned for each cohort.

Rev.02, 1 March 2018 Confidential Page 3 of 8

Document: TDOC-0056125 **Version:** 1.0; CURRENT; Most-Recent; Effective

Status: Effective

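### SAP 5.6 and 7 summarize effectiveness in per-protocol eyes and, in the available text, leave out the all-implanted-eyes summary that Protocol 8.3.1 requires

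*SAP*

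**What the plan says.** The protocol defines two analysis sets. Section 8.2.1 reads "The Implanted-Eye Population consists of eyes with successful HMIOL implantations during surgeries". Section 8.2.2 takes those same eyes, removes the ones with a major protocol deviation, and says that the resulting PP set "will be considered the primary population for effectiveness outcomes". Section 8.3.1 then assigns the endpoints to both: "Each endpoint will be analyzed based on the Implanted-eye Population and PP Population".

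The SAP also names two sets, but a different pair. Section 7 defines a Safety Population (attempted implantation, including aborted attempts) and a Per-Protocol Population, which it describes this way: "Eyes with successful HMIOL implantation that do not have major protocol deviations (such as improperly enrolled in the study or lens power calculation errors"). Section 5.6 places effectiveness in the second: "Effectiveness endpoints will be summarized in the per-protocol population for each cohort at each study visit for which they are available". Section 7 repeats that assignment. On the relation between the documents, SAP 2 states: "Analyses described here expand on and supersede those described in the Investigational Plan".

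The SAP's contents list shows a section 8 on sensitivity analyses and a section 9 on subgroup analyses. The available text goes from section 7 to section 10.

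**The concern.** The primary objective (Protocol 2.0) is to evaluate visual and refractive outcomes. The PP set drops eyes with major deviations, and the only examples given are improper enrolment and errors in lens power calculation. A power error is not incidental to this objective: it puts the eye off target and so acts directly on UCDVA and MRSE. BCDVA is measured with correction and should be little affected.

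That is a reason to show both sets side by side, as the protocol planned. PP can reasonably be the primary set, but the Implanted-Eye summary tells the reader how much the exclusions matter. If the visible SAP text is followed as it stands, that comparison is lost and no reason is given. In a study with no hypothesis test, the descriptive tables are the result, so the choice of eyes in them matters.

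**Working it through.** No figure in the plan needs reproducing. The main check is a comparison of the texts.

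**Step 1. Sets required for effectiveness.**

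| | Implanted-Eye | PP |
|---|---|---|
| Protocol 8.2.2 and 8.3.1 | yes | yes (primary) |
| SAP 5.6 and 7, available text | not named | yes |

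The primary set agrees. The second set is the one that drops out.

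**Step 2. Does another visible SAP set bring it back?**
- SAP 4 has "All HMIOL Eyes Cohort: Defined as all study eyes implanted with the study device". These are essentially the Implanted-Eye eyes, but it is a cohort and not an analysis population. SAP 5.6 applies PP within each cohort, so its effectiveness table would still lack the excluded eyes.
- The Safety Population is wider, because it includes aborted attempts, and its use is specified: "The intraoperative and postoperative AEs and device deficiencies, slit lamp examination, dilated fundus examination, and IOP will be summarized based on the safety population". UCDVA and MRSE are not named for it in SAP 5.4, 5.5 or 7. The only acuity item there is a loss of 2 or more lines of BCDVA (5.4).
- Protocol 7.1 lists UCDVA, MR and BCDVA under a safety heading, and SAP 5.6 names no endpoints. The SAP therefore does not say outright which set these three measures belong to.

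**Step 3. What could be recovered without a new table?** For continuous measures, SAP 5.1 reports the number of observations and the number of eyes not reported. SAP 5.2 summarizes enrolment and SAP 5.3 the eyes available at each visit. Subtracting the PP counts from these should give the number of excluded eyes roughly. The missing-data reasons in 5.3 do not include exclusion from PP, and no visible table gives the reasons for exclusion or the outcomes of the excluded eyes.

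**Step 4. How far could the figures move? (Illustration on assumed inputs.)** The documents give no exclusion rate and no outcomes for excluded eyes. Let f be the fraction excluded, assumed to be 3%, 5% or 10%.

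*Mean MRSE (a listed endpoint).* Let d be the mean in excluded eyes minus the mean in retained eyes. The all-eyes mean is the retained mean plus f × d, so PP mean − all-eyes mean = −f × d. With d = 1 D (assumed), the shift is 0.03, 0.05 or 0.10 D. Its sign depends on the sign of d.

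*Within 1 D of target.* This is not a listed endpoint, although SAP 5.1 allows continuous measures to be split into categories. Take b = 0.85 in all implanted eyes, borrowed from the benchmark in Protocol 1.0 for conventional surgery in normal eyes. Let m be the share of excluded eyes that miss 1 D. The PP rate is (b − f(1 − m)) / (1 − f).

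| m | f = 3% | f = 5% | f = 10% |
|---|---|---|---|
| 0 | 84.5% | 84.2% | 83.3% |
| 0.15 (same as all eyes) | 85.0% | 85.0% | 85.0% |
| 0.5 | 86.1% | 86.8% | 88.9% |
| 1 | 87.6% | 89.5% | 94.4% |

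For example, f = 10% and m = 0.5 gives (0.85 − 0.05) / 0.90 = 88.9%. The shift runs from −1.7 to +9.4 points. The top value needs 0.10 / 0.15, or two-thirds, of all misses to come from excluded eyes. The table shows the mechanism and its sign; it does not estimate what happened in this study.

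**The case against.** The strongest objection is that the deciding text may simply be absent from the available copy. A repeat of the effectiveness tables in all implanted eyes would fit naturally under Sensitivity Analyses, and that section is listed but not available. This stands. A reader might infer that the sponsor abandoned the Implanted-Eye analysis; the documents do not support that. They support only that 5.6 and 7 neither contain it nor point to it.

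The second objection is that SAP 2 settles precedence, so there is no open contradiction, and that 5.6 never restricts effectiveness to PP alone. This is partly right. The point is an unexplained narrowing, not two instructions that cannot be reconciled. However, SAP 2 says both that the SAP expands on the protocol's analyses and that it supersedes them, and an analyst who follows 5.6 and 7 has no instruction to produce the second set.

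Third, there are partial safeguards. Protocol 4.10 requires the date and reason of each deviation to be recorded, 8.2.2 has sponsor clinical personnel review deviations before analysis, and 9.1.1 calls for masking as far as possible. A reader might infer that eyes could be removed because of a poor refraction. No passage says so, and the documents do not support it. What remains is that neither document defines a lens power calculation error or says that it is judged without sight of postoperative refraction.

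Fourth, the study is descriptive and unpowered (Protocol 8.1), and SAP 4 says that any formal tests are not meant to support regulatory approval. This stands and limits the weight of the point.

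**Conclusion.** The point holds as a gap between Protocol 8.3.1 and the available text of SAP 5.6 and 7, and it should be fixed. Confidence is medium because SAP sections 8 and 9 could not be read.

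The size of any effect is unknown. The direction is probably favourable for refractive accuracy after primary implantation, because power errors would tend to put eyes off target. It is uncertain for signed mean MRSE and for Cohort 2. The assumed-input figures should not be read as a finding that the PP results are inflated by any stated amount. Nor are the exclusions wholly hidden: the number should be roughly recoverable from the reported counts, although the reasons and the excluded eyes' outcomes are not. The primary population is unchanged, and no test, error rate or power calculation is affected.

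**What to change.** First check SAP section 8. If it already specifies effectiveness summaries in all implanted eyes, a cross-reference from 5.6 resolves the question of the second set. Otherwise:

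1. Add the Implanted-Eye Population to SAP 7, as defined in Protocol 8.2.1.
2. In SAP 5.6, name UCDVA, MRSE and BCDVA as the effectiveness endpoints, and report them in the Implanted-Eye Population beside PP for each cohort, keeping PP primary.
3. In either case, list by cohort the number of eyes excluded from PP and the reason for each exclusion, unless section 8 already provides this.

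A one-sentence definition of a lens power calculation error, shared by both documents, would help as a clarification. It does not correct a demonstrated error.

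The cost is some SAP wording and one extra set of descriptive tables from data already collected. The Implanted-Eye refractive figures may look slightly less favourable than the PP figures.

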Corneal modifications have been performed on tens of millions of people across the world with some form of refractive surgery (e.g. LASIK). For example, in the U.S. (where the most extensive data exists) 11.5M Americans have had corneal refractive surgery and over the next two decades many will need cataract surgery. LASIK increases the likelihood for residual refractive error post cataract surgery due to inaccurate IOL power calculations with biometry. There is hesitation among many ophthalmologists to repeat LASIK for RRE after cataract surgery because the FDA has not specifically evaluated the safety and effectiveness of repeated LASIK in this setting. All the risks associated with the original LASIK procedure apply to retreatment, along with the increased potential for epithelial ingrowth, corneal ectasia and less robust nomograms for IOL selection for post cataract patients.

Furthermore, even for eyes that have not undergone prior corneal refractive surgery, the FDA has not specifically evaluated the safety and effectiveness of corneal refractive procedures (e.g., astigmatic keratotomy, LASIK, PRK, etc.) to address RRE following lens replacement surgery, so the use of approved lasers for this purpose in the U.S. is considered off-label and the risks are not well characterized. For example, it is unclear how optical aberrations that might be present with an IOL in place are increased by aberrations induced by corneal refractive procedures, how likely corneal refractive procedures are to induce irregular astigmatism and worsen dry eye that is induced by cataract surgery, and whether corneal refractive procedures could create potential complications related to cataract surgery wound healing or IOL stability.

Furthermore, cornea based interventions do not address the root cause of RRE after cataract extraction (imprecise IOL power selection) and expose the patient to a new and independent set of possible adverse events. Thus, it would be desirable to be able to correct or modify the optical result without the need to irreversibly and unpredictably alter corneal tissue following cataract extraction.

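### The per-protocol exclusion for lens power calculation errors is applied once per eye, so an error at primary implantation also removes that eye's outcomes after optic exchange

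*SAP*

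**What the plan says.** SAP section 7 admits to the per-protocol (PP) set "Eyes with successful HMIOL implantation that do not have major protocol deviations (such as improperly enrolled in the study or lens power calculation errors". The same section adds: "The effectiveness endpoints will be summarized based on the per-protocol population". Section 5.6 spells out the reach: "Effectiveness endpoints will be summarized in the per-protocol population for each cohort at each study visit for which they are available".

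SAP section 4 divides Cohort 2 follow-up into two periods. One covers the visits between cataract extraction and exchange. The other is "Post-Optic Exchange, comprising visits following optic exchange", with the last pre-exchange visit as its baseline. No separate PP rule is given for either period.

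Protocol 8.2.2 has the same exclusion and says that this set "will be considered the primary population for effectiveness outcomes". Protocol 8.3.1 also requires each endpoint in the Implanted-Eye Population, which has no deviation exclusion. The SAP text supplied defines only the Safety and PP populations, and SAP section 2 says that its analyses supersede those of the protocol.

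On the exchange itself, SAP section 4 gives the choice to the investigator together with the patient, who "decide if an optic exchange in the study eye is in the best interests of the subject based on refractive outcome and target". Protocol 3.3.4 and the Cohort 2 assessment schedule give the exchange its own power determination.

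**The concern.** The exclusion is tied to the reason for having an exchange. An error in the primary power calculation tends to leave a refractive miss, and a refractive miss is a ground for exchange. The protocol's introduction names "the root cause of RRE after cataract extraction (imprecise IOL power selection" as the problem that corneal procedures leave untouched and that the modular lens is designed to address.

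A primary calculation error is a fair reason to leave an eye out of a PP summary of primary implantation. It does not make the later exchange invalid, because a new power is determined for that procedure. With one flag per eye, the first procedure's deviation removes the second procedure's result.

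Visual and refractive outcomes of optic exchange are part of the primary objective (protocol 2.0). The study is descriptive, so the Cohort 2 summary is itself the finding. If the set behind it leaves out eyes with a clear reason for exchange, it describes a selected part of the procedure's intended use.

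**Working it through.** **Tracing the rule.** The plan has no figure to reproduce: it states no power, effect size, exchange rate or error rate. The first check is therefore logical. PP status of a Cohort 2 eye under the visible SAP text, and under a per-procedure rule:

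| Eye | Now: pre-exchange | Now: post-exchange | Per procedure: pre | Per procedure: post |
|---|---|---|---|---|
| Major-deviation error, primary calculation | out | out | out | in |
| Major-deviation error, exchange calculation | out | out | in | out |
| Ordinary refractive miss, no deviation | in | in | in | in |
| Monovision intolerance, no deviation | in | in | in | in |

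The first two rows rest on the unqualified term in SAP section 7. Both calculations are scheduled and the rule does not choose between them. On its plain wording an exchange error would also cost the eye its valid pre-exchange data.

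**Illustrative size.** Inputs:
- 200: the cap on subjects in protocol 3.1, used here as one study eye each. This is an assumption, since the synopsis allows implantation in both eyes.
- 16%: the upper background rate of additional surgical correction in protocol 1.0. It is not an exchange rate for this lens. 0.16 × 200 = 32 exchanged eyes.
- s, the share of exchanged eyes excluded for a calculation error: 10%, 25%, 50% (assumed).
- Mean improvement in absolute MRSE: 1.25 D in excluded eyes, 0.50 D in retained eyes (assumed).

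Mean over all exchanged eyes = (excluded × 1.25 + retained × 0.50) / 32. The PP mean is 0.50 D throughout.

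| s | Excluded / retained | Mean, all eyes | PP shortfall |
|---|---|---|---|
| 10% | 3 / 29 | 18.25/32 = 0.57 D | 0.07 D |
| 25% | 8 / 24 | 22/32 = 0.69 D | 0.19 D |
| 50% | 16 / 16 | 28/32 = 0.88 D | 0.38 D |

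A wider contrast, 1.7 D against 0.6 D with s of 10–30%, gives 0.6(1 − s) + 1.7s = 0.71 to 0.93 D against 0.60 D in PP. That is 0.11/0.71 = 15% to 0.33/0.93 = 35% too low. In general the shift is s × (mean of excluded − mean of retained), so these results restate the assumed inputs. With 5% exchanged (10 eyes), PP would keep 9, 8 or 5.

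**Direction.** The shortfall above needs an absolute-change summary. The protocol lists MRSE, and SAP section 5.6 specifies no absolute change. With signed MRSE, myopic and hyperopic corrections offset and the shift could be near zero. For accuracy against target the bias could run the other way: if large power changes are harder to hit, dropping them flatters the result.

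**Precision.** With the same SD of 0.5 D in every set, the 95% half-width t × SD/√n is 0.18 D for 32 eyes and 0.19, 0.21 or 0.27 D for 29, 24 or 16. That comparison fails once the two groups differ in mean. At s = 25% the pooled variance is 0.25 + 0.25 × 0.75 × 0.75² = 0.355, so the SD is about 0.60 and the half-width for 32 eyes about 2.04 × 0.60/√32 = 0.22 D, no narrower than PP. A loss of precision is not established.

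**The case against.** The strongest reply is that a reader might infer that Cohort 2 loses the very eyes the exchange exists to correct. The documents do not support that. The introduction attributes refractive misses to current biometry and surgical methods in general: up to 55% miss target by at least 0.5 D, and 14–24% exceed 1 D with manufacturer constants. Those are not protocol deviations. The PP rule lists calculation errors beside improper enrolment, as a kind of major deviation. Ordinary misses therefore stay in PP, as do eyes exchanged for monovision intolerance. The excluded subset is undefined and may be small or empty. This objection stands and limits the point to some of the target eyes.

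Second, a reader might infer that the lost outcomes appear nowhere. Protocol 8.3.1 would report them in the Implanted-Eye Population, and the SAP never expressly cancels that analysis. The SAP contents also list sections on sensitivity and subgroup analyses (8 and 9) whose text is not in the material supplied, so a second effectiveness set there cannot be ruled out. This stands in part. The visible SAP defines no such population and claims precedence. Even if the analysis survives, the set that the protocol calls primary for effectiveness keeps the selection.

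Third, dropping major deviations is what a PP set is for, and no hypothesis test depends on it. That is true, but it does not justify carrying a deviation in one procedure over to the result of another.

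Fourth, splitting PP by period seems to clash with the SAP baseline, which is a pre-exchange visit. The fix has to deal with this, and can.

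**Conclusion.** The point holds in a limited form. On the visible text, an eye with a primary power calculation error classed as a major deviation contributes to no PP effectiveness summary, before or after exchange, although the exchange has its own power calculation. Such eyes are likely exchange candidates, so the loss from Cohort 2 is selective.

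The number of eyes and the direction of bias cannot be derived from the documents. The 0.07–0.38 D and the 15–35% rest wholly on assumed exchange rates, error shares and changes in refraction. They show how the bias would work, and a reader should not take them as its expected size. It would also be wrong to conclude that most of the exchange population is lost or that the correction is certainly understated. The conclusion assumes that SAP sections 8 and 9 contain nothing that restores these eyes. The change is worth making because it is cheap and bears on part of the primary objective, but it does not undermine the study as a whole.

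**What to change.** In SAP section 7 and protocol 8.2.2, apply major deviations per procedure:

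- A calculation error at primary implantation removes the eye from PP only for the primary-implantation summaries (All HMIOL Eyes, Cohort 1, Cohort 2 pre-exchange).
- An error in the exchange calculation removes it only from the post-exchange summaries.
- State which calculation the term covers and define what counts as an error, as distinct from an ordinary refractive miss.
- Keep the last pre-exchange value as the baseline for change in every eye retained after exchange, even where that eye is left out of the PP pre-exchange table.
- Report the number of eyes excluded for this reason, by cohort and period.
- Carry the protocol's Implanted-Eye analysis into the SAP, at least for Cohort 2 post-exchange outcomes.

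The cost is a few sentences, one period-specific PP flag and one further set of Cohort 2 tables. The drawback is that PP denominators will differ between the pre- and post-exchange tables, which a footnote with the counts would explain.
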